9.7.5. Healthcare Resource Utilization and Cost

All-cause HCRU and MM-related HCRU (ie, HCRU with a diagnosis code or treatment for MM) will be measured as the total number of IP, OP, ED, and pharmacy claims that occurred over the follow-up period. Medical claims will only be counted once per day to estimate

visits, pharmacy claims will count all claims including multiple on the same day. Additionally, the total length of IP stays will be reported among patients with at least one IP visit. Given the recency of the study period, costs will not be adjusted for inflation. As the number of HCRU claims will vary by patient follow up time, results will also be reported as PPPM.

HCRU and associated costs will be measured across four different time periods. The first time period will be from 180 days prior to index date to one day prior to the index date, the second time period will be the index date until last recorded dose, the third time period will be during the step-up dosing period, the fourth time period will be the index date until discontinuation with an allowable 8-week gap of the index drug.

Patients will be censored at the earliest of death, next treatment (CAR-T, BsABs, bendamustine or belantamab), the end of continuous closed-claim coverage, or the latest data at the time of the specified analysis.

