3	TTD	Time in months from first administration until last administration prior to treatment discontinuation (continuous). Treatment discontinuation is defined as an 8-week gap in elranatamab (or for the exploratory analysis, teclistamab therapy), next treatment after index treatment (CAR-T, BsABs, bendamustine or belantamab), or death.	Index date to the end of follow-up. Follow-up will be defined based on the censoring criteria described in Section 9.7.4
Health care resource utilization and costs			
4	All-cause IP visits	Medical claim for IP (non-ED) visit (dichotomous)	180 days prior to index date to 1 day prior to index date
		Number of IP (non-ED) visits (continuous)	Step-Up Dosing Period Index date to end of follow-up. Follow-up will be defined two ways to account for gaps in elranatamab use. See Section 9.7.5 for censoring criteria
4	IP visits from the IP table	Medical claim for IP (non-ED) visit sourced from the IP table (dichotomous)	180 days prior to index date to 1 day prior to index date
		Number of IP (non-ED) visits sourced from the IP table (continuous)	Step-Up Dosing Period Index date to end of follow-up. Follow-up will be defined two ways to account for gaps in elranatamab use. See Section 9.7.5 for censoring criteria
4	IP visits from the Non-IP table	Medical claim for IP (non-ED) visit sourced from the Non-IP table where place of service indicates an IP setting (dichotomous)	180 days prior to index date to 1 day prior to index date

		Number of IP (non-ED) visits sourced from the IP table place of service indicates an IP setting (continuous)	Step-Up Dosing Period Index date to end of follow-up. Follow-up will be defined two ways to account for gaps in elranatamab use. See Section 9.7.5 for censoring criteria
4	All-cause OP visits	Medical claim for non-IP/non-ED visit (dichotomous)	180 days prior to index date to 1 day prior to index date
		Number of non-IP/non-ED visits (continuous)	Step-Up Dosing Period Index date to end of follow-up. Follow-up will be defined two ways to account for gaps in elranatamab use. See Section 9.7.5 for censoring criteria
4	All-cause ED visits	Medical claim for ED visit (dichotomous)	180 days prior to index date to 1 day prior to index date
		Number of ED visits (continuous)	Step-Up Dosing Period Index date to end of follow-up. Follow-up will be defined two ways to account for gaps in elranatamab use. See Section 9.7.5 for censoring criteria
4	All-cause pharmacy claims	Pharmacy claim (dichotomous)	

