Lymphocyte count	Baseline characteristic - Lab	Claims data	An event in the lab results table where the result_abbrev is lymphocytes count and result_units are thousand per µL	
Monocyte count	Baseline characteristic - Lab	Claims data	An event in the lab results table where the result_abbrev is monocytes count and result_units are thousand per µL	
Platelet Count	Baseline characteristic - Lab	Claims data	An event in the lab results table where the result_abbrev is platelets and result_units are thousand per µL	
ImmunoglobulinA	Baseline characteristic - Lab	Claims data	An event in the lab results table where the result_abbrev is IGA and result_units are mg per dL	
ImmunoglobulinG	Baseline characteristic - Lab	Claims data	An event in the lab results table where the result_abbrev is IGG and result_units are mg per dL	
ImmunoglobulinE	Baseline characteristic - Lab	Claims data	An event in the lab results table where the result_abbrev is IGE and result_units are IU per mL	
ImmunoglobulinM	Baseline characteristic - Lab	Claims data	An event in the lab results table where the result_abbrev is IGM and result_units are mg per dL	
Bone marrow plasma cell percent	Baseline characteristic - Lab	Claims data	An event in the GDD table where the test is bone_marrow and result_units are percent	
M-Protein	Baseline characteristic - Lab	Claims data	An event in the GDD table where the test is m-spike and result_units are mg/dL	
Use of premedication	Outcome - Dosing and Administration Patterns	Claims data	HCPSCS (Mapped via SEER [Dexamethasone only] or Athena – OHDSI using generic name): J0136, J0137, J0134, J0131, C9283, G6039, J1200, Q0163, J8540, J1100, J1094	SEER (2024) ELREXFIO Label

PFIZER CONFIDENTIAL

Redacted

			Generic names (and associated NDCs): Acetaminophen, Dexamethasone, Diphenhydramine	
Inpatient	Baseline characteristic, Outcome - HCRU	Claims data	Any event in the inpatient table or an event in the non-inpatient table where acute_subacute is “acute inpatient” or where utilization type is “professional services” and service subcategory contains the term “hospital/ip encounter”	
OP	Baseline characteristic, Outcome - HCRU	Claims data	Any event in the non-inpatient table where utilization type is outpatient and service subcategory is not “emergency dept encounter”	
ED	Baseline characteristic, Outcome - HCRU	Claims data	Any event in the non-inpatient table where utilization type is “outpatient” and service subcategory is “emergency dept encounter”	

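### The combined inpatient visit count is a count of claim days, because no rule merges inpatient claims into an admission; the Annex 2 outpatient rule also conflicts with Table 3

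*Protocol*

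**What the plan says.** Section 9.7.5 states that resource use "will be measured as the total number of IP, OP, ED, and pharmacy claims that occurred over the follow-up period". For medical claims its only de-duplication rule is "Medical claims will only be counted once per day to estimate" visits.

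Annex 2 gives three routes into the inpatient category. The first two are "Any event in the inpatient table or an event in the non-inpatient table where acute_subacute is" recorded with the acute value. The third brings in lines from clinicians' billing: "or where utilization type is “professional services” and service subcategory contains the term “hospital/ip encounter".

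Table 3 (Section 9.3) then lists "Number of IP (non-ED) visits (continuous", all-cause, with a matching MM-related row. It also splits the all-cause count by source table. One of those rows is "Medical claim for IP (non-ED) visit sourced from the Non-IP table where place of service indicates an IP setting (dichotomous", but its continuous counterpart says that the visits come from the IP table. Total duration of inpatient stays is a further outcome in Table 3 and Section 9.7.5.

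For outpatient use, Table 3 takes the residual: "Medical claim for non-IP/non-ED visit (dichotomous". The Abstract says the same. Annex 2 is narrower: "Any event in the non-inpatient table where utilization type is outpatient and service subcategory is not" an emergency department encounter. The Annex 2 emergency department rule also requires utilization type outpatient.

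**The concern.** Counting at most one claim per day is a sensible way to estimate outpatient and emergency department visits. An admission, however, can carry qualifying claims on several dates: a facility record, acute-inpatient events, and professional lines for care during the stay. Under the stated rule each further date adds an inpatient visit.

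Inpatient use by place of service is part of primary Objective 3. A reader of the report will take visits per patient, or visits PPPM, as a measure of how often patients were hospitalised. If the number instead follows length of stay and billing frequency, it partly repeats the length-of-stay outcome and leaves admissions unmeasured.

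A separate problem lies in the outpatient rule. If Annex 2 is programmed as written, professional-service lines that meet none of its setting definitions leave the outpatient count, and with it total resource use and total cost.

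**Working it through.** The plan gives no figure to reproduce, so the check applies its own rules to one hypothetical admission.

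**Inputs**

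- Counting unit: a calendar day with at least one qualifying medical claim (Section 9.7.5).
- Qualifying inpatient events: the three kinds in Annex 2.
- Merging rule: none in Section 9.3, Section 9.7.5 or Annex 2.
- Step-up window: index date to Day 8 (Table 4). The numbering of the index date is not stated, so D = 8 days if it is Day 1 and D = 9 days if it is Day 0.
- Month length: 30.4375 days, stated in Section 9.7.4 for time to discontinuation and assumed here for PPPM.
- Length of stay and frequency of professional claims: not in the protocol, so varied as assumptions.

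**Visits per admission**

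V = number of distinct dates with a qualifying event; the number of admissions is 1.

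- All qualifying claims on one date: V = 1 at any length of stay.
- 5-day stay: V = 2 with claims on 2 days, V = 5 with claims every day.
- 8-day stay: V = 4 with claims on 4 days, V = 8 with claims every day.

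The ratio of counted visits to admissions therefore runs from 1 to L, where L is the number of days in the stay with a qualifying claim.

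**PPPM in the step-up window**

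PPPM = V × 30.4375 / D.

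| Claim days V | D = 8 | D = 9 |
|---|---|---|
| 1 (also the value if stays are counted) | 30.4375/8 = 3.80 | 30.4375/9 = 3.38 |
| 3 | 91.3125/8 = 11.41 | 91.3125/9 = 10.15 |
| 5 | 152.1875/8 = 19.02 | 152.1875/9 = 16.91 |
| 8 | 243.5/8 = 30.44 | 243.5/9 = 27.06 |

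**Which outcomes are exposed**

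- Exposed: the continuous combined inpatient counts (all-cause and MM-related), the total counts that include them, and their PPPM values, in all four assessment periods and in both cohorts.
- Not inflated by the counting rule: yes/no inpatient outcomes, which need only one claim, and summed inpatient costs, which add amounts and not visits.

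**Outpatient definition, side by side**

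Annex 2 names professional services and outpatient as values of the same field, utilization type. A professional-service line that is neither a hospital encounter nor flagged acute inpatient then classifies as follows:

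- Annex 2 inpatient: no.
- Annex 2 outpatient: no, because the utilization type is not outpatient.
- Annex 2 emergency department: no, for the same reason.
- Table 3 outpatient: yes by residue, unless it is an emergency department line.

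The two definitions cannot both be applied. Table 3 builds total resource use and total cost from inpatient, outpatient, emergency department and pharmacy claims, so a line without a setting is in neither total. The documents do not say how many such lines exist.

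**The case against.** The strongest reply is that nothing in the protocol says professional hospital claims are billed daily, or how they are dated. That stands: daily billing is an assumption, and the lower end of the range is no inflation at all. A reader might infer that every multi-day admission will be counted many times over, or that an eightfold excess is expected. The documents do not support either.

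Second, the plan already separates inpatient-table visits from those found in the non-inpatient table, and it reports total inpatient days. This limits the harm, because the inpatient-table count leaves out the professional lines. It does not correct the combined counts. The split is also blurred by the continuous non-inpatient-table row that names the wrong source table, and the protocol does not say whether inpatient-table rows are one per stay.

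Third, the measure is described as claims used to estimate visits, and stay construction might be set out in a statistical analysis plan or in the table shells listed in Annex 1. The protocol, however, itself fixes both the once-per-day rule and the inpatient definition, and Section 9.8 says that it will be strictly followed. A duration of stays cannot be computed without identifying stays, so the missing link between stays and visits is a gap in rules that the protocol has chosen to state.

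Fourth, a reader might infer that the distortion is greatest during step-up. That is unsupported. The short window caps the number of claim days, and stays at baseline or later may be longer. The PPPM values look large mainly because a window of 8 or 9 days is scaled to a month; the ratio of 1 to 8 carries the information.

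**Conclusion.** The point holds in a limited form. As written, the combined inpatient visit counts under primary Objective 3 are counts of claim days, with a ratio to admissions anywhere from 1 to the number of claim days in the stay. The 8-day illustration (3.8 PPPM for a stay, 3.8 to 30.4 for 1 to 8 claim days) rests on assumed claim frequency, one stay within the window and the assumed month length; it is not an estimate of the actual bias. It would be wrong to conclude that inpatient costs or the proportion of patients with any inpatient visit are inflated, since the counting rule does not touch them.

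The outpatient conflict between Table 3 and Annex 2 is a direct contradiction and does not depend on billing frequency. Its effect on outpatient use, total use and total cost cannot be sized from the documents. Both matters should be corrected before the final report.

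**What to change.** 1. In Section 9.7.5 and Annex 2, merge inpatient-flagged facility and professional claims with overlapping or contiguous dates into stays. Prespecify the allowed gap and justify it, because a wide gap would join a prompt readmission to the preceding stay.
2. Count stays as inpatient visits, and report inpatient days as a separate outcome derived from the same stays. State when a merged stay is MM-related, for example if any of its claims carries an MM code or MM treatment.
3. Keep once-per-day counting for outpatient and emergency department visits.
4. Correct the source table named in the continuous row for inpatient visits from the non-inpatient table.
5. Align the Annex 2 outpatient rule with the residual definition in Table 3. Assign professional lines for emergency department encounters to the emergency department first; otherwise a residual rule would move them into outpatient.

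The cost is a short text change, one stay-building step in the programming and a re-run on data already held, ahead of the final report planned for 28 February 2026. Reported inpatient visit counts will stay the same or fall, and outpatient, emergency department and total figures may rise. If results already delivered used the literal rules, the report should say that they are not comparable.

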Population: This study will include adult (≥ 18 years old) patients with an International Classification of Diseases, tenth revision (ICD-10) code for RRMM (defined as MM ICD-10 codes: C90.0x). The study cohort will include patients with RRMM who initiate elranatamab between 14 August 2023 (US approval date) and end of data (defined as the latest data available, at the time of the specified analysis). Exploratory analyses will also include a teclistamab-exposed cohort, which will include patients with RRMM who initiate teclistamab between 14 August 2023, and the end of data. The index date for patients in each cohort will be defined as the date of the first prescription or medical claim for elranatamab or teclistamab. Patients will be required to have at least 180 days of continuous closed-claims enrollment before the index date.

Variables: Variables used to define eligibility will include elranatamab, MM diagnosis, and observability.

Variables to define demographic and clinical characteristics will include, but are not limited to, age, sex, race/ethnicity, region, Charlson Comorbidity Index (CCI), and prior infections.

Prior treatment history will be captured based on the use of National Comprehensive Cancer Network (NCCN) guideline-recommended treatments, which include chimeric antigen receptor T cell therapy (CAR-T), PIs, and IMiDs.

HCRU and costs will be described overall and by place of service, including inpatient (IP) visits, outpatient visits (OP, defined as non-IP/non-ED), emergency department (ED) visits, and pharmacy claims. Additionally, HCRU and imputed costs will be reported as all-cause and MM-related.

Adverse events (AEs) will include cytokine release syndrome (CRS), immune effector cell-associated neurotoxicity syndrome (ICANS), peripheral neuropathy, and infections. Effectiveness outcomes will include TTNT/D and OS.

Country of Study: US

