Milestones: Data analysis will begin after protocol finalization by 15 August 2024. There will be one initial set of results and four subsequent quarterly refreshes with updated data throughout 2025. At the end of implementation, a final report will be generated by 28 February 2026.

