6. MILESTONES

Milestone	Planned Date
Start of data collection	15 August 2024
Registration in The Heads of Medicines Agencies (HMA)-European Medical Agency (EMA) Catalogues of Real World Date (RWD) studies	26 July 2024
Interim results delivery	23 September 2024
Full results delivery	15 November 2024
Full result refresh 1	15 January 2025
Full result refresh 2	09 April 2025
Full result refresh 3	09 September 2025
End of data collection	20 November 2025
Full result refresh 4	20 December 2025
Final study report	28 February 2026

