9.2. Setting

This study will evaluate adult patients with RRMM who initiate elranatamab. Patients will enter (i.e., index) on the first observed elranatamab claim between 14 August 2023 and the end of data (defined as the latest data at the time of the specified analysis). Limited eligibility criteria will be applied.

Study Period: Start of data availability (01 January 2016) to the end of data

MM diagnosis window: Start of data availability (01 January 2016) to index date

Index date: First elranatamab claim after initial MM diagnosis

Observability: At least 180 days of continuous closed-claims medical and pharmacy enrollment prior to index (inclusive)

[figure not shown]
Baseline period for MM-related treatments and MM-related comorbidities: MM diagnosis to one day prior to index date (unless otherwise specified)

CCI and baseline HCRU assessment window: 180 days prior to index date to index date.

Follow-up: Index date until death, the earliest of the end of data, or end of continuous enrollment (unless otherwise noted). Alternative censoring criteria will be applied for certain outcomes (such as OS, TTD, and TTNT/D); see [Section 9.7](#) for more details.

Figure 1 reflects the time periods of interest in the study cohort.

Figure 1. Study Schematic for Patients Receiving Elranatamab

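### Recency is not a sufficient reason to leave costs unadjusted for inflation when the cost window can reach about 33 months and no price year is stated for the imputed costs

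*Protocol*

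**What the plan says.** Section 9.7.5 sets the rule and gives one reason for it: "Given the recency of the study period, costs will not be adjusted for inflation". The same section measures costs in four periods. The first runs "from 180 days prior to index date to one day prior to the index date". The other three start at index: one ends at the last recorded dose, one covers the step-up period, and for the longest "the fourth time period will be the index date until discontinuation with an allowable 8-week gap of the index drug". Results are also given per patient per month.

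The calendar limits come from other sections. Section 9.2 lets patients index "between 14 August 2023 and the end of data", and the abstract says the end of data is "defined as the latest data available, at the time of the specified analysis". The abstract also announces "four subsequent quarterly refreshes with updated data throughout 2025", and section 6 dates the end of data collection as "20 November 2025".

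Section 9.4 says the data vendor imputes costs from what its sources supply and from public Medicare fee-for-service pricing tools. It does not say which year's prices are applied. Section 9.2.1 gives the teclistamab cohort the same index window. Section 9.7 says that the cohorts are reported separately and not formally compared.

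**The concern.** Pooling nominal costs is reasonable when they all fall within a short period. Recency is a different property: a window can end recently and still be long. Under version 2.0 the end of data moves with each refresh, so the cost window is no longer short.

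The exposed output is the set of baseline and post-index cost figures for Objective 3. Within every patient, baseline comes before follow-up. If costs carry the prices of the service year and prices rise, the later figure is inflated relative to the earlier one, and the error has the same sign in every patient. A larger sample or a further refresh would not average it out. Because section 9.4 gives no price year, a reader of the report could not tell whether this applies.

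**Working it through.** The protocol gives no figure for price growth or for the price basis, so there is no planned figure to reproduce. The check is date arithmetic plus an assumed range of growth.

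**Inputs from the protocol**
- First possible index date: 14 August 2023 (section 9.2).
- Baseline: 180 days before index (section 9.7.5).
- Latest possible end of data: 20 November 2025 (section 6). This is an upper bound, because the end of data is not tied to that date.
- First full results delivery: 15 November 2024 (section 6).
- 1 month = 30.4375 days (section 9.7.4).

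**Assumption:** price growth *r* of 2%, 3% or 5% a year. The documents give none.

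**Step 1: length of the cost window**
- Earliest baseline day: 14 August 2023 − 180 days = 15 February 2023.
- To 20 November 2025: 1,009 days; 1,009 / 30.4375 = 33.1 months, touching 2023, 2024 and 2025.
- To the first full results delivery, for comparison: 639 days, or 21.0 months at most.
- If the usable data end 3 or 6 months before 20 November 2025 (assumed lags): 917 or 825 days, or 30.1 or 27.1 months.
- Longest possible follow-up, 14 August 2023 to 20 November 2025: 829 days, or 27.2 months.

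**Step 2: drift between a patient's baseline and follow-up**

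Take each period at its midpoint. With follow-up of *F* months, the gap in years is (90/30.4375 + *F*/2)/12, and the drift is (1 + *r*)^gap − 1. For *F* = 12, the gap is (2.96 + 6)/12 = 0.75 years, and 1.02^0.75 − 1 = 1.5%.

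| Follow-up | Gap (years) | 2% a year | 3% a year | 5% a year |
|---|---|---|---|---|
| 3 months | 0.37 | 0.7% | 1.1% | 1.8% |
| 6 months | 0.50 | 1.0% | 1.5% | 2.5% |
| 12 months | 0.75 | 1.5% | 2.2% | 3.7% |
| 27.2 months (maximum) | 1.38 | 2.8% | 4.2% | 7.0% |

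**Step 3: the two ends of the window**

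Over 1,009 / 365.25 = 2.76 years, prices on the first and last possible days would differ by 5.6%, 8.5% or 14.4% at 2%, 3% or 5% a year. No planned estimate compares those two days, so these figures do not measure bias in any reported result.

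**Step 4: dependence on the price basis**

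Steps 2 and 3 apply only if costs are imputed at service-year prices. If the vendor prices every claim at one reference year, each drift figure is zero.

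**The case against.** The strongest reply is that nothing in the protocol shows costs to be in mixed-year dollars. They are imputed, and imputation at a single fee-schedule year would already put them on a constant basis. This stands. A reader might infer from the no-adjustment sentence that dollars of different years are in fact added together, but section 9.4 does not support that. It supports only the statement that the price year is not given. The reply does not rescue the reason, however: if costs were already at one price level, that would be the justification to state.

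A second reply is that the rule is disclosed, the study is descriptive, and no baseline-to-follow-up cost difference is specified as an estimate. This is also true, and it limits the weight of the point. Even so, the same measures are reported before and after index, and readers will set them side by side. Most of any contrast will reflect the index drug itself, which is absent at baseline by definition, so price drift would be a small part of it.

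A reader might also infer that the comparison of elranatamab with teclistamab is distorted. Both cohorts index in the same calendar window and are not formally compared, so a price effect between them would arise only if uptake dates differed, and the documents do not say whether they do.

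Finally, the drift is small against sampling error. With the 56 patients cited in section 9.5 and an assumed coefficient of variation of 1, the standard error of a mean cost is about 1/√56 = 13%. This stands as a reason for low priority, although section 9.5 foresees updated data, and a drift of constant sign does not shrink as patients are added.

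**Conclusion.** The point holds as a minor one. The cost window can run from 15 February 2023 to as late as 20 November 2025, and recency does not justify leaving a primary cost outcome unadjusted over up to 33.1 months when no price year is stated. If costs are imputed at service-year prices and prices rise by 2% to 5% a year (both assumptions), on-treatment costs would be raised relative to baseline by about 1.0% to 2.5% for 6 months of follow-up and 1.5% to 3.7% for 12 months. If one reference year is already used, the effect is nil. The 5.6% to 14.4% between the two ends of the window should not be quoted as the size of the problem.

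**What to change.** First confirm with the vendor which year's prices the imputation uses, and state it in section 9.4. The change to section 9.7.5 then depends on the answer.

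- If service-year prices are used, replace the sentence with:

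> Costs in all baseline and follow-up windows and both cohorts are expressed in one common year's US dollars (2025) using a published medical-care price index or single-year imputation, with unadjusted costs as a secondary presentation.

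- If one price year is already used, give that as the reason for not adjusting, and do not index again. Indexing costs that are already constant would create the distortion it is meant to remove.

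The cost is one query to the vendor, one or two sentences and, if conversion is needed, one multiplier per service year or a single-year imputation. The drawbacks are that an index must be chosen, a general medical-care index may not follow oncology drug prices closely, and cost figures from earlier refreshes would have to be restated.
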